## VI. BIOSTATISTICAL ANALYSIS

Power analysis: Based on longitudinal exercise capacity data from our lab, extensive sets of power analyses were performed. For the main analysis (acute subjects only), there will be 3 groups of subjects (FES-RT, wait-list and arms-only-RT) and measures at baseline, 3 months, 6 months, except for visceral adiposity (only at baseline and 6 months). The primary analysis (below) will include the three groups and will have as predictors two indicator (dummy) variables for two of the groups, and indicators for the 3 month and 6 month time points and interactions between the time points and the group indicator variables; this will be estimated as a linear mixed model. The only random effect will be for subject. In addition, for the fourth aim, the analysis will only include those entered into FES-RT at the outset, i.e., the FES-RT with acute SCI and all

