## PARTNERS HUMAN RESEARCH COMMITTEE

### DETAILED PROTOCOL

volunteers with chronic SCI. The main analysis will consist of comparisons across time with injury duration as a covariate.

Given logistical constraints, we began with the assumption that data on 50 acute SCI subjects (out of 60 recruited - a ~15% dropout rate) would be advantageous if that sample size allowed us to find differences that are substantively meaningful. This group would be allocated (randomly; see below) as 40% to FES-RT and 30% to each of wait-list and arms-only-RT. We also checked other total sample sizes and allocation rules (e.g., data from 20 in each group, data from 25 in FES and 15 in each of the other two groups). In addition, 25 individuals with chronic SCI would provide sufficient power to detect meaningful (e.g., >15%) differences between acute and chronic SCI at the same power outlined below.

These calculations were performed assuming an alpha of 0.05 and a correlation between baseline and 6 month measure of about 0.7; unless the correlation was very different from 0.7 (e.g., 0.25), there was little difference in the results. This shows that we will have sufficient power under this plan with a sample size of 50 acute SCI subjects and allocation of 20/15/15. Subjects will be randomized at the ratio of 1.33:1:1 to each of the three groups by a randomization plan constructed by the project statistician. The investigator will have no knowledge of group assignment until the time of subject enrollment. During the study, there can be no blinding of the subject or the investigator, however all measures will be obtained by an individual blind to subject group assignment.

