*Primary data analysis:* The primary analysis will test whether the FES-RT has 'better' values of the outcome variables at 6 months post-baseline. A general linear mixed model with a random effect for subjects will be used to conduct an intent-to-treat analysis. The main predictors will be indicator variables for group with the FES-RT group as the reference group and indicators for each of the other two groups, the time at which the outcomes were measured and treatment group by time interactions; menstrual status (with men coded the same as women who are not menstruating) will be included as a dummy variable; for the insulin resistance measure, body weight/fat changes will be included as a predictor. In a secondary analysis, we will include interactions terms between the group indicators and the 3 month indicator. In addition, similar models to the above will be estimated for secondary outcomes.

*Checking and Sensitivity Analyses:* It is important to ensure that data idiosyncrasies do not impact the results and that the results are generalizable. We will check for systematic differences between the model and the data using graphs, such as comparisons of predicted and observed values of the outcome variable, and other standard diagnostics. An extension of this idea is to simulate new sets of data based on our model and use the simulated data as a reference test group by comparing this to the observed data; we do this to look for situations in which the data appear different

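### Aims 1-3: the mixed model gives each randomised arm its own baseline mean; it is valid, but for the group-by-6-month interaction it loses about 15% of the information at the plan's assumed correlation

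*Combined protocol and SAP*

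**What the plan says.** Section VI (Biostatistical Analysis) describes the model twice.

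- **Power analysis paragraph.** Outcomes are measured at baseline, 3 and 6 months (visceral adiposity at baseline and 6 months only). The linear mixed model has two group indicators, 3- and 6-month indicators, and "interactions between the time points and the group indicator variables". Subject is the only random effect.
- **Primary data analysis paragraph.** "The main predictors will be indicator variables for group with the FES-RT group as the reference group". Time and group-by-time terms follow, but the group-by-3-month terms are then assigned to a secondary analysis. The listed covariates are menstrual status and, for insulin resistance, change in weight or fat.

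The baseline value of the outcome is not a covariate in either paragraph, and nothing constrains the arms to a common baseline mean. The further predictors named under Checking and Sensitivity Analyses (gender, severity and level of injury) do not include it.

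The planning assumptions are "a correlation between baseline and 6 month measure of about 0.7" and "a sample size of 50 acute SCI subjects and allocation of 20/15/15".

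**The concern.** Randomisation makes the expected baseline means of the three acute arms equal. A model that still estimates a separate baseline mean for each arm ignores this. With complete data and both interactions present, its group-by-6-month coefficient is simply the difference in mean change from baseline. Unless r is close to 1, that is a noisier estimate of the same effect than one adjusted for baseline.

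With 15 to 20 analysed subjects per arm and a total that the plan says is set by logistics, precision is scarce and the baseline values are already being collected. Arms this small will also often differ at baseline by chance, and a change score does not handle that difference optimally.

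**Working it through.** **Inputs.** r of about 0.7, alpha 0.05 and 20/15/15 come from the power paragraph of section VI. The plan states no SD, effect size or power, so variances are in units of the outcome variance (SD = 1, equal across arms and visits) and a two-sided test is assumed. Other covariates are ignored.

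**The plan's own figures.** The stated power cannot be reproduced, because no power value or effect size is given. The allocation can: 40/30/30% of 50 is 20/15/15, and 20/15 = 1.33, matching the stated ratio. Section III gives 25/18/17 instead. That needs reconciling separately, but the variance ratio below does not depend on arm sizes.

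**Variance, both interactions in the model.** Multiply each factor by (1/20 + 1/15) = 0.1167.

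- Planned (difference in change): 2(1-r) = 0.60. SE = sqrt(0.60 × 0.1167) = 0.265 SD.
- Common baseline mean, or ANCOVA: 1-r² = 0.51. SE = sqrt(0.51 × 0.1167) = 0.244 SD.
- Ratio: (1-r²)/[2(1-r)] = (1+r)/2 = 0.85. The share of information lost is (1-r)/2.

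| r | Planned | Adjusted | Loss |
|---|---|---|---|
| 0.25 | 1.50 | 0.94 | 37.5% |
| 0.5 | 1.00 | 0.75 | 25% |
| 0.7 | 0.60 | 0.51 | 15% |
| 0.8 | 0.40 | 0.36 | 10% |
| 0.9 | 0.20 | 0.19 | 5% |

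At r = 0.7 the planned analysis of 50 carries the information of 50 × 0.85 = 42.5 adjusted subjects. It would need 50/0.85 = 58.8 subjects to match an adjusted analysis of 50.

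**Small samples.** The 15% treats the covariance as known. Two sets of 40,000 simulated two-visit trials at 20/15/15 and r = 0.7 gave:

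- change 0.0696 against ANCOVA 0.0609, a loss of 12.5%;
- change 0.0706 against ANCOVA 0.0615 (13%) and against a common-baseline mixed model 0.0608 (14%).

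**If the group-by-3-month terms are left out.** Under a random intercept, the three-visit contrast becomes 6 months minus the mean of baseline and 3 months. Its factor is 1.5(1-r) = 0.45. Without group main effects it is 1 - 2r²/(1+r) = 0.424. The loss is 1 - 0.424/0.45 = 6%, for a different estimand. Visceral fat has no 3-month value, so its loss stays at 15%.

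**Chance imbalance.** Given an observed baseline difference D, the change contrast has expectation (true effect) - (1-r)D. D has SD sqrt(0.1167) = 0.34. At r = 0.7 a 1-SD imbalance therefore shifts the estimate by 0.30 × 0.34 = 0.10 SD. Simulated slopes on D were -0.29 for change and 0.01 for ANCOVA.

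**Power, for illustration.** At an assumed true difference of 0.76 SD (not in the documents), 20 versus 15, power is about 81% with the change contrast and about 86% with ANCOVA.

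**The case against.** The strongest reply is that nothing here is an error. Free group-by-time terms are conventional, and the planned estimator is unbiased over randomisations with no sign of a type I error problem. That stands: this is a gain in efficiency, not the repair of an invalid analysis.

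Four further points carry weight.

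- **Imbalance.** A reader might infer that baseline imbalance goes uncorrected. It does not: the change contrast subtracts the whole difference, which is too much by the factor (1-r). The resulting 0.10 SD is under half of the 0.265 SD standard error.
- **The assumed correlation.** The power work used exercise-capacity data, not the Aim 1-3 outcomes. The DXA paragraph quotes ±1% precision for regional fat, so a higher r is possible there, and with it a loss nearer 5-10%.
- **Which contrast is tested.** The primary analysis paragraph speaks of outcome values at 6 months. A reader might infer a test of the 6-month level difference, with factor 1 against 0.51 and a loss of 49%. The documents do not specify that test, and the interaction terms point towards change, so the larger figure is not claimed.
- **What counts as baseline.** Section V allows 2 to 12 weeks of strength training before FES rowing, and an extra assessment for anyone needing more than eight weeks to reach the baseline FES-VO2max test. Wait-list subjects have their rowing test soon after enrolment. A common mean is justified by randomisation only for a measurement taken before arm-specific training. This objection does not defeat the change, but it does put a condition on it.

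**Conclusion.** The point holds as an essentially free gain in precision for Aims 1-3. At r of about 0.7, with both interactions in the model and the group-by-6-month coefficient as the test, the planned analysis loses 15% of the available information in large samples and about 12.5-14% at 20/15/15. The loss is larger at lower r and smaller at higher r. If the paragraph that makes the group-by-3-month terms secondary governs, the loss is about 6% for three-visit outcomes, and 15% is secure only for visceral fat.

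These figures assume equal variances, the random-intercept correlation structure, complete data and a true pre-training baseline. The 0.76 SD used for power is an assumption, but the variance ratio does not depend on it. The documents do not support calling the planned analysis biased or invalid.

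**What to change.** For Aims 1-3, in section VI:

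1. Reconcile the two model descriptions so that both group-by-3-month and group-by-6-month interactions are in the primary model.
2. Name the group-by-6-month coefficients as the primary test.
3. Drop the group main effects so that the randomised arms share one baseline mean. For visceral fat, use ANCOVA of the 6-month value on baseline.
4. Define baseline in every arm as the first, pre-training measurement, not the extra assessment under Study Assessments. Early enrollees may have done leg strengthening before any assessment. That offer is not tied to arm, so the constraint remains reasonable if uptake does not depend on assignment, and uptake should be recorded.
5. Do not apply the constraint to Aim 4, whose acute and chronic groups are not randomised.

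The cost is SAP wording, a definition of the baseline measurement and a small change of code. No new data are needed.

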## PARTNERS HUMAN RESEARCH COMMITTEE

### DETAILED PROTOCOL

Participants will be excluded if they have: 1)Hypertension (blood pressure >140/90 mmHg), 2) significant arrhythmias, 3) coronary disease, 4) diabetes, 5) renal disease, 6) cancer, 7) epilepsy, 8) current use of cardioactive or antidepressant medications, 9) family history of significant arrhythmia or sudden cardiac death 10) orthostatic hypertension with symptomatic fall in blood pressure > 30 mmHg when upright 11) current grade 2 or greater pressure ulcers at relevant contact sites, 12) other neurological disease, 13) peripheral nerve compressions or rotator cuff tears that limit the ability to row, 14) history of bleeding disorder, 15) regular use of tobacco, 16) current deep venous thrombosis, 17) severe spasticity (that prevent rowing movements), 18) severe autonomic dysreflexia, 19) implanted electronic cardiac device (pace maker, cardiac defibrillator), 20) ventilator-dependent condition, 21) sensations that prevent the use of the electrical stimulation, 22) other medical contraindications to vigorous exercise.

The American College of Sports Medicine's Guidelines for Exercise Testing and Prescription 9th edition will be followed as the standard of care along with the clinical specialists' opinion (Drs. [name] and [name]) regarding any additional pre-participation screening needed prior to beginning this vigorous exercise training program.

Pregnant and nursing women are not eligible for this study because of the potential risk to the fetus from radiation that goes along with the DXA scan. Women who are able to become pregnant must agree to use contraceptive methods while participating in the study. Acceptable contraceptive methods are: a) hormonal methods (birth control pills, patches, injections, vaginal ring or implants); b) barrier methods (condom or diaphragm, with a foam, cream or gel spermicide); c) intrauterine device (IUD); or d) abstinence (no sex). Women are considered unable to become pregnant if they are menopausal and have not had a menstrual period for at least one year or if they have had a hysterectomy (surgical removal of your uterus and/or ovaries).

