## PARTNERS HUMAN RESEARCH COMMITTEE

### DETAILED PROTOCOL

#### **V. STUDY PROCEDURES**

Volunteers who enroll in the study before 3-months from their injury date will have a partial screening visit in which informed consent and detailed health history will be obtained(all other assessments will be scheduled after they reach at least 3-month post SCI. Once recruited for the study volunteers (that are at least 3-months post injury) will visit the laboratory for a health screening session to further determine eligibility. This two may require one or two visits depending on the ability to schedule with the physician. It will include obtaining informed consent, detailed health history, PROMIS 57 questionnaire, a standard physical exam (ASIA exam and Ashworth Scale) performed by a physician (if necessary), height and weight measurements, resting blood pressure, electrocardiogram (EKG) and FES-device test.

Note: If an ASIA exam and Ashworth Scale have previously been performed by a physician and results can be obtained, those medical records may be used and the physical exam will not be necessary during screening.

Subjects may also be asked to provide additional medical records or may need further testing to determine their eligibility and the safety of their participation in this program which includes regular vigorous exercise. These additional tests may or may not be covered by insurance. The subject will be responsible for obtaining any additional testing and providing the program with medical records or results.

Approximately 40% of spinal cord injured women have amenorrhea for an average of eight months. Therefore, menstrual status will be tracked and explored as a potential covariate. A prospective menstrual diary will be collected for three months prior to each data acquisition time-point. For each monthly diary, women will mark the day of the month when bleeding occurred and rate the heaviness of blood flow (spotting to heavy). If no bleeding occurred during a particular month or the menstrual period, this will be indicated. Bleeding patterns will be used to define normal, irregular, or absent menstrual cycles.

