#### **2) ARMS-ONLY-RT GROUP(Acute SCI only)**

The arms-only-RT group will commence exercise training upon enrollment. Training sessions will be 3 times per week for 26 weeks. To parallel the FES-RT, the initial training sessions will also consist of 6 sets of arms-only rowing for five minutes at 60% of VO2peak with a work-to-rest ratio of 2:1 and progress over the six months to an exercise intensity of 75-85% maintained for 30 minutes performed three times each week. The arms-only-RT group will also perform the FES-leg strength training protocol as described above during their six months of arms-only training. During this time they will not use the FES-device on the rowing ergometer. Strengthening the leg muscles during the arms-only period will lessen leg muscle atrophy and allow faster progress in FES-row training when they enter that phase of the study. A maximum arms-only rowing test will be performed at baseline. This will be repeated after three months of training and training intensity will be adjusted to maintain the training stimulus at the same relative intensity. A maximum arms-only rowing test will be performed at the end of the six months of training to determine increases in fitness. Subsequently, after the six months of arms-only-RT, subjects will begin the FES-RT as described above.

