## PARTNERS HUMAN RESEARCH COMMITTEE

### DETAILED PROTOCOL

from what we would expect by using the model to predict the data. We will also check whether any important predictors have been left out of the model, for example, gender or severity of SCI or level of SCI. These will be tested by including them in revised versions of the model and testing whether the model is substantively improved. It is also important to explore the ‘missingness’ of data. The model we plan to use assumes that missing data are “missing at random.” This can be checked in several ways including comparing the characteristics of observations with and without missing values. More importantly, we can check whether our results would change if the data is “missing not at random” in several ways. For certain outcome variables, it may be the case that subjects who are either at the high end or the low end are more likely to be missing. For example, people at baseline who are very fat or very lean may be more likely to drop out. This can be checked by using constrained multiple imputation where we constrain our imputations to one end of the adiposity range. Comparing the results based on the constrained imputation to the unimputed results gives us a sensitivity analysis.

A second type of sensitivity analysis was originally suggested by Rubin and has been extended by Carpenter, Kenward and White who suggest weighting each imputed result (rather than Rubin’s standard “rules” of averaging the results), where the weight depends on the assumed departure from the MAR assumption. This technique relies on the imputations covering a fairly wide range of values (we would use 100 imputations) but this can be checked and additional data sets imputed if the range is too narrow. Carpenter, *et al.*, provide a graphic method of checking whether the range is wide enough. Finally, if dropouts are much more common than missing an occasion and then returning, we will estimate a pattern-mixture model. However, if there are many people who miss the 3 month measure, but not the 6 month measure, we will not pursue this strategy. A fourth issue deals with the variance structure of the model. Our prime model assumes that the variances are the same across groups. This will be tested by estimating a model with heterogeneous variance structures by group (this is available in some statistical packages, including Stata or SAS).

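### The primary model's single menstrual-status dummy codes men with non-menstruating women and has no sex term, so its coefficient mixes sex with menstrual status and can move the 6-month contrast if current status is entered

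*Combined protocol and SAP*

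**What the plan says.** The primary analysis (Section VI, Primary data analysis) is a linear mixed model with group, time, their interactions and a random subject effect. It adds that "menstrual status (with men coded the same as women who are not menstruating) will be included as a dummy variable". No sex term is listed.

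Under Checking and Sensitivity Analyses the plan states: "We will also check whether any important predictors have been left out of the model, for example, gender or severity of SCI". Such predictors are added to revised versions of the model and judged by whether the fit improves.

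Section V gives the source of the covariate: "A prospective menstrual diary will be collected for three months prior to each data acquisition time-point". It also gives the reason for collecting it: "Approximately 40% of spinal cord injured women have amenorrhea for an average of eight months". There the variable has a weaker role, since "menstrual status will be tracked and explored as a potential covariate", and it has three levels: "Bleeding patterns will be used to define normal, irregular, or absent menstrual cycles".

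Two further passages matter. In Section V, "The arms-only-RT group will commence exercise training upon enrollment". In Section III, the accepted contraceptive methods include "hormonal methods (birth control pills, patches, injections, vaginal ring or implants".

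**The concern.** One coefficient has to do two jobs. Men and amenorrhoeic women share a code, so the dummy separates menstruating women from everyone else. With no sex term, any male-female difference in visceral fat, lipids or wall thickness loads on it.

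This matters for the treatment comparison if the dummy changes over time. A woman who resumes menses would then have her follow-up value adjusted by a coefficient that is largely a sex difference. If resumption differs by arm, part of that adjustment enters the group-by-time contrast. A current-value covariate is also post-randomisation: if training acts partly through menstrual recovery, adjusting for recovery removes part of the effect being tested.

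The baseline value has its own difficulty. A prospective three-month diary cannot precede baseline for a woman who starts at enrollment, and no fallback is given. The plan also does not say how irregular cycles, or bleeding altered by hormonal contraception, map to a single dummy.

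**Working it through.** **Inputs from the plan:** 20/15/15 subjects analysed, correlation about 0.7, random subject intercept only, 40% of women amenorrhoeic. **Assumptions, not in the documents:** women are 20% or 40% of subjects; the sex difference is 1 SD (or 1.5 SD); the true menstrual effect is zero; amenorrhoeic women resume menses at 80% in FES-RT and 30% in comparators, or at 50% in all arms. The plan states no figure for this covariate, so there is none to reproduce.

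**1. The coefficient when status never changes.** It is the mean of menstruating women minus the mean of everyone else. With 20% women, 12% of subjects are coded 1. The other 88% include 8% who are amenorrhoeic women. With women 1 SD lower: -1 + 8/88 = -0.91 SD. With 40% women: -1 + 16/76 = -0.79 SD. The true menstrual effect is zero in both cases.

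**2. The coefficient when some women resume.** Within-woman information, whose true effect is zero, pulls it towards zero. Simulating the planned model with 80% against 30% resumption gives about -0.65 SD (20% women) and -0.55 SD (40% women). A wider grid of assumptions gave -0.50 to -0.90 SD.

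**3. The shift in the 6-month change contrast.** It is approximately the share of women × 0.4 × the difference in resumption × the size of the coefficient.

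| Women | Sex difference | Resumption | By hand | Simulated |
|---|---|---|---|---|
| 20% | 1 SD | 80% v 30% | 0.20 × 0.4 × 0.5 × 0.65 = 0.026 | 0.02 SD |
| 40% | 1 SD | 80% v 30% | 0.40 × 0.4 × 0.5 × 0.55 = 0.044 | 0.04 SD |
| 40% | 1.5 SD | 80% v 30% | 0.40 × 0.4 × 0.5 × 0.81 = 0.065 | 0.06 SD |
| 20% or 40% | 1 SD | 50% v 50% | 0 | 0.00 SD |
| 20% or 40% | 1 SD | no change | 0 | 0.00 SD |

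An extreme case (50% women, resumption 100% against 0%) gives 0.09 to 0.11 SD, or 0.13 to 0.15 SD at a 1.5 SD sex difference.

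**4. Scale.** The variance of change per subject is 2(1 - 0.7) = 0.6. For 20 against 15, SE = √[0.6 × (1/20 + 1/15)] = √0.07 = 0.26 SD. A shift of 0.04 SD is 0.04/0.26, about 15% of one SE. Across the wider grid the null rejection rate was 0.04 to 0.08 with the dummy and 0.04 to 0.07 without it.

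**5. A single trial.** A zero average shift still leaves noise. With 50% resumption in all arms and a 1 SD sex difference, the 95th percentile of the absolute shift is about 0.09 to 0.11 SD.

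**6. Missing baseline diaries.** Suppose women are 20% of subjects and all lose their baseline rows. With two time-points (visceral adiposity), the mixed model's change estimate is 0.94 × (6-month mean, complete subjects) + 0.06 × (6-month mean, subjects without baseline) - (baseline mean, complete subjects). Its variance, times n, is (0.94² + 1 - 2 × 0.94 × 0.7)/0.8 + 0.06²/0.2 = 0.7095 + 0.018 = 0.7275. Then √(0.7275/0.6) = 1.10, a 10% larger SE. With three time-points the same calculation gives 0.7059, and √(0.7059/0.6) = 1.08. If half the women are affected, the rise is 4 to 5%.

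**7. After the fix.** With sex and baseline-only menstrual status as separate terms, the 6-month change contrast equals the no-dummy contrast in every scenario (shift 0.000 SD).

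**The case against.** The strongest reply is that the coding alone does not bias the treatment comparison. A reader might infer that the dummy is necessarily measured after randomisation and so carries the sex difference into the 6-month contrast. The documents do not support that. There is a diary before baseline as well as before follow-up, and the plan does not say which value is entered. A baseline value is constant over time and cancels from change. Expected bias needs three things together: a time-varying value, a sex difference in the outcome, and menstrual change that differs by arm. The documents establish none of them. Even with all three, the shift is a small fraction of one SE in the main scenarios, and at 20% women only about four of 50 subjects (50 × 0.2 × 0.4) are amenorrhoeic at baseline. All of this stands.

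The gender check is a second reply. It stands only in part: it is a data-driven revision that leaves the primary model and the coding of men unchanged.

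On baseline diaries, a reader might treat the affected women as lost altogether and put the SE increase at √(50/40), or 12%. That is too high, because their follow-up rows still contribute to a mixed model. Nor does the plan say that such rows are dropped. Subjects may also enroll before three months post-injury, with no assessments until then, so some women could have part or all of a diary; a detailed health history is taken at screening too.

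The covariate also has a stated rationale, so there is no need to discard it.

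**Conclusion.** The concern holds as a fault in how the primary model is specified. It is not a demonstrated bias in the treatment effect. The coefficient confounds sex with menstrual status whichever value is entered. Whether the 6-month contrast is affected depends on a choice that the plan leaves open. If current status is used, the expected shift is 0 with equal change across arms and about 0.02 to 0.04 SD (0.06 SD at a 1.5 SD sex difference) with 80% against 30% resumption, against an SE of about 0.26 SD. These sizes rest on assumed shares of women, sex differences and resumption rates.

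Possible adjustment for part of a training effect that acts through menstrual recovery is a further risk, and it was not quantified. The baseline diary is unobtainable as specified for women who start at enrollment. Sections V and VI disagree on whether the covariate is exploratory or required, and on three levels or one dummy. Different defensible readings would give different primary results from the same data. The change is worth making because it costs almost nothing.

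**What to change.** In Section VI, Primary data analysis:

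- Add sex as its own baseline term.
- If menstrual status is kept, enter only the baseline value, coded within women. Take it from recall or the health history where no diary exists.
- State how irregular cycles and users of hormonal contraception are coded.
- Move menstrual status at 3 and 6 months to an exploratory analysis.

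Then align Section V with Section VI on the role of the covariate and its number of levels. The cost is one extra model term, some wording and possibly one recall question at baseline. No other new data are needed.
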